6.2.11 Assessment of Adverse Events

AEs are collected from the time of signing the informed consent form and throughout the study duration. New systemic and skin AEs will be recorded on the appropriate source document and eCRF.

6.2.12 Investigator Skin Assessment

The investigator will perform a visual skin assessment of bruising, erythema, and edema at the randomization visit and at the End of Study (or early discontinuation) visit. Any adverse events including application site reactions will be documented on the appropriate eCRF page and must be followed until resolution or medically stable.

At the End of Study (or early discontinuation) visit, the entire surface area of the outer upper arm where the two patches were applied will be assessed for the following skin signs or symptoms.

Any findings with an intensity rating of 1 (Mild intensity), 2 (Moderate intensity), or 3 (Severe intensity) must be recorded as an adverse event in the eCRF and followed to resolution. The investigator will use the definitions of AE Severity Ratings for Mild, Moderate, Severe, Life-Threatening (Section 8.2.1.3) to assess the Severity of the AE.

For further instructions, photographs and descriptors are in Photograph and Appendix 1 (Investigator Assessments – Rating for Bruising, Erythema, Swelling and Photographs).

1.1.1.1 Bruising

The Bruising assessment will be performed by the investigator at Visit 3 End of Study or Early discontinuation.

Bruising assessments (visual rating) will be performed using the following ratings:

Symptom	Intensity Rating (circle)
Bruising where	0 = Clear
C213 was applied?	1 = Mild intensity
	2 = Moderate intensity
	3 = Severe intensity

1.1.1.2 Erythema and Edema

Erythema and Edema will be assessed by the investigator at Visit 3 End of Study or early termination.

The following ratings will be used to describe the amount of erythema and edema indicative of irritation:

Symptom	Rating (circle)
Skin Erythema	0 = Clear
where C213 was applied?	1 = Mild intensity
	2 = Moderate intensity
	3 = Severe intensity

Symptom	Rating (circle)
Skin Edema where	0 = Clear
C213 was applied?	1 = Mild intensity
	2 = Moderate intensity
	3 = Severe intensity

Adverse Events of Special Interest: Any site reactions requiring further evaluation or care (e.g., by a dermatologist), as well as those resulting in scarring are considered adverse events of special interest. If these reactions are detected, the de-identified photograph of the patch application site and contralateral arm (containing the date of photograph, visit number and subject number) must be transmitted to the sponsor within 24 hours of the clinic visit for further dermatological evaluation.

6.2.13 Medication Compliance

Subject compliance with study drug administration will be reviewed at the End of Study (or early discontinuation) visit. The applicator and any unused patches will be collected.

7 STATISTICS

A full description of the statistical analyses to be performed at study completion will be provided in a Statistical Analysis Plan (SAP), which will be finalized prior to database lock and unblinding of the study.

Unless otherwise noted, significance tests of treatment differences will be tested at the two-sided 0.05 level.

7.1 Analysis Populations

Modified Intent-to-Treat (mITT) Population

All randomized patients who have a qualifying headache and at least one post-application pain score recorded within the first 15 minutes post-application will be included in the mITT population. This is the primary population for efficacy analyses and patients will be analyzed based on their randomized treatment.

Safety Population

The safety population will include all patients who received any amount of study drug. All safety analyses will be performed using this population, analyzed as treated.

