6.1.2 Visit 2, Day 1 Randomization

- Perform physical exam, including weight
- Perform investigator skin assessment of the upper arm where patches are intended to be applied
- Record vital signs: temperature, respiratory rate (RR), blood pressure (BP), and heart rate (HR)
- Record concomitant medications, including medication taken to treat cluster headaches
- Urine pregnancy for all WOCBP
- Record Adverse events
- Train the subject on how to apply the patches to the upper arm with the demo applicator and have the subject practice applying the demo patches to his/her arm 2-3 times (more is allowable, if necessary)
- Review the definition of a qualifying cluster headache for the study with the subjects
- Record that the subject can apply patches with the applicator unaided
- Reconfirm subject's eligibility based on inclusion/exclusion criteria
- Randomize subject
- Dispense CTM kit that includes the applicator and one dose (each dose consists of 2 patches) as assigned by the RTSM in Medidata

- Provide instructions for scheduling the next visit within 1-8 days of experiencing and treating a qualifying cluster headache with C213
- Remind the subject that if rescue therapy is required, rescue therapy other than a triptan or ergot is permitted at or after 20 minutes post study drug administration.
- Provide eDiary training necessary and dispense the eDiary

6.1.3 Double-Blind Treatment Phase: Day 1 through up to 48 Weeks [336 Days + or – 7 days]

Subjects will have up to 48 weeks to confirm and treat a qualifying cluster headache. Subjects will be instructed to complete the eDiary at the time of a suspected cluster headache. Once the eDiary confirms that the subject has a "qualifying" cluster headache, the subject will follow the steps provided to self-administer the study drug.

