6.1.4 Pregnancy Tests (every 4 weeks \pm 7 days)

- A urine pregnancy test will be collected on WOCBP every month from the day of randomization during the double-blind period to ensure the subject is not pregnant prior to administration of study medication.
 - Due to the COVID-19 pandemic, a urine pregnancy test kit will be sent to WOCBP for in-home testing on a monthly basis. The Investigator (or designee) will contact the subject to review and document the result.

6.1.5 Investigator (or designee) Phone Contact to Subjects (every 4 weeks \pm 3 days)

Following randomization, the investigator (or designee) will contact the subject monthly to assess for:

• Adverse events, concomitant medications and to provide study related reminders regarding eDiary use and/or C213 application instructions in advance of administering study medication for the qualifying cluster attack.

6.1.6 Investigator (or designee) Phone Contact to Subject– Following application of C213 (+ 2 days)

The investigator (or designee) will contact the subject within 2 days after C213 application to assess for:

• Adverse events and to schedule the subject for a final visit 1-8 days after C213 application.

6.1.7 Visit 3 - Day 1-8 Following Treatment of Cluster Headache / End of Study (or Early Discontinuation) Visit (+3 days)

The following procedures will be performed at the Day 1-8 / end of study (or early discontinuation):

- Collect the applicator and any unused patches and perform drug accountability
- Perform physical exam, including weight
- Record vital signs: temperature, respiratory rate (RR), blood pressure (BP), and heart rate (HR)
- Collect blood (4-hr fasting) for clinical laboratory measurements including clinical chemistries, coagulation, hematology, and serum pregnancy for WOCBP
- Collect serum pregnancy for all WOCBP
- Perform 12-lead electrocardiogram (ECG)
- Collect and review subject's eDiary data with the subject for the following:

 Subject compliance with study drug treatment and/or rescue therapy use
- Investigator Skin Assessment
- Record concomitant medications
- Review of adverse events

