8.1 Reporting Period

Collection of systemic and skin AEs will be initiated after the ICF has been signed and will conclude when the post-study procedures are completed (or Early Discontinuation). The investigator will also report to the Medical Monitor and Pharmacovigilance any SAEs that come to his/her attention that occur within 30 days after study drug administration.

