8.2 Adverse Event Definitions

8.2.1 Adverse Events (Adverse Experiences)

An AE is any untoward medical event that occurs in a clinical investigation, where a subject is administered a medicinal (investigational) product or medical device, and which does not necessarily have a causal relationship between the event and the treatment. An AE can be any unfavorable and unintended sign or symptom, including clinically significant abnormal laboratory result, concomitant illness, or worsening of an existing medical condition.

A Treatment Emergent Adverse Event (TEAE) is an event that emerges during treatment having been absent pre-treatment or worsens relative to the pre-treatment state.

Collection of systemic and skin AEs will be initiated after the ICF has been signed and conclude when the post-study procedures are completed (or Early Discontinuation). This includes the time between screening and the first dosing.

Abnormal laboratory tests that are clinically significant, as determined by the investigator, should be reported as AEs if:

- the test result is associated with accompanying symptoms;
- the test result requires additional diagnostic testing or medical/surgical intervention;
- the test result leads to discontinuation from the study, significant additional concomitant drug treatment, or other therapy;
- the test result is considered to be an AE by the investigator or sponsor.

Merely repeating an abnormal test, in the absence of any of the above conditions, does not constitute an AE. Any abnormal test result that is determined to be an error does not require reporting as an AE.

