#### 10. SAFETY AND TOLERABILITY ANALYSIS

The safety analysis will be run on the Safety population. The analysis of safety assessments in this study will include summaries or data listings of the following safety and tolerability data collected for each subject:

- Adverse Events including Serious Adverse Events
- Clinical Laboratory Investigations including coagulation studies
- Concomitant Medications
- Vital Signs
- Physical exam including height and weight
- Investigator visual skin assessments
- Electrocardiogram Parameters
- Pregnancy Tests

Protocol: CP-2019-001 Page 21 of 26

Final Version 1.0

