#### **10.1.3** Deaths

A listing of deaths will be provided for the Safety Population.

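### The death listing covers dosed subjects only, so a death in a randomised subject who never doses is left out, and the plan does not settle whether the SAE listing includes such subjects

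*Protocol*

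**What the plan says.** **Collection.** Protocol 6.2.11: "AEs are collected from the time of signing the informed consent form and throughout the study duration". Protocol 8.1 agrees: "Collection of systemic and skin AEs will be initiated after the ICF has been signed". Protocol 8.2.1 settles the pre-dose interval: "This includes the time between screening and the first dosing". That interval can be long. Protocol 6.1.3: "Subjects will have up to 48 weeks to confirm and treat a qualifying cluster headache". Events are sought actively during the wait. Protocol 6.1.5: "Following randomization, the investigator (or designee) will contact the subject monthly to assess for" adverse events, among other items. Protocol 8.3.1 requires every SAE, whatever its cause, to be reported and entered on the AE page of the eCRF. Protocol 8.2.1.4 requires an SAE associated with study procedures to be recorded as such.

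**Reporting.** Protocol 7.1 and SAP 6 define the Safety population as those who received any amount of study drug, and both add: "All safety analyses will be performed using this population, analyzed as treated". SAP 10 opens with "The safety analysis will be run on the Safety population" and describes that analysis as made up of summaries or listings, with AEs and SAEs first among the items. SAP 10.1.3: "A listing of deaths will be provided for the Safety Population". SAP 10.1.2 promises an SAE listing and names no population. SAP 10.1 says that the AE listings show all AEs, with treatment-emergent ones flagged. SAP 8.1 tabulates disposition, including randomised subjects and reasons for withdrawal.

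**The concern.** Events are collected in a wider set of subjects than the set in which they are reported. The difference is the randomised subjects who never apply a patch, and such subjects are foreseeable. Entry requires only one cluster period in the previous 12 months (inclusion criterion 4). Dosing requires a severe attack that meets Protocol 6.1.3.1 within 48 weeks, with no triptan or ergot in the preceding 24 hours. In the meantime these subjects are under study procedures, including practice with demonstration patches on the arm at Visit 2.

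Readers take a death listing in a study report as complete. With a dosed-only filter it may not be, even though the event is in the database. The same would apply to the SAE listing if the programmer follows the general rule.

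**Working it through.** The plan gives no figure on this point, so the check is a trace through the text. Take a subject who is randomised, waits, never has a qualifying attack, and dies or has an SAE during the wait.

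1. **Is the event collected?** Yes. Protocol 6.2.11, 8.1 and 8.2.1 cover the time from consent to first dosing, and 8.3.1 puts every SAE on the AE eCRF page.
2. **Is the subject in the Safety population?** No. No study drug was received (Protocol 7.1, SAP 6).
3. **Is a death in the death listing?** No. SAP 10.1.3 names the Safety Population. This step needs no inference.
4. **Is an SAE in the SAE listing?** Not settled.
   - *Pointing to exclusion:* Protocol 7.1 and SAP 6 put all safety analyses on dosed subjects, and SAP 10 applies this to listings as well as summaries. SAP 7.1.2 admits the safety data of withdrawn subjects to the Visit 3 summaries only as the Safety population definition allows. SAP 8.3 asks for demographics in all randomised subjects, so the SAP names a wider set when it wants one, and it does so for no safety output. SAP 7.3.1 and 10.1 classify AEs only by whether they occurred before the patch, which leaves no category for a subject who never had one.
   - *Pointing to inclusion:* SAP 10.1.2 names no population, while 10.1.3 and the laboratory listing in 10.2 do. SAP 10.1 says that the AE listings show all AEs.
   - *Result:* exclusion is the more natural reading, but the text does not compel it.
5. **Does the event appear anywhere else in the planned outputs?** Possibly, in disposition. Protocol 3.2.6.1 requires the site to establish whether a withdrawal was due to an AE, and SAP 8.1 tabulates the reasons. A death or AE that ended participation could therefore appear as a count under a reason, without the details an event listing gives, such as onset, outcome or causality. An SAE that did not end participation would leave no trace there.

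| Event in a never-dosed subject | Collected | Event listing | Disposition |
|---|---|---|---|
| Death | Yes | Excluded by name | At most a reason count |
| SAE that ends participation | Yes | Ambiguous, probably excluded | At most a reason count |
| SAE that does not end participation | Yes | Ambiguous, probably excluded | None |

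**The case against.** The strongest case on the other side has three parts. A dosed-only Safety population is conventional, and it is right for treatment-emergent tables. The SAP names a population where it means to restrict a listing, so silence in 10.1.2 and the all-AEs sentence in 10.1 may be meant to include everyone. And SAEs do not go unseen: they go to pharmacovigilance whatever their cause (Protocol 8.3.1), and the investigator reports them to the IRB (8.3.1.1).

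The first part stands, and the fix leaves those tables alone. The second stands as far as making the SAE listing ambiguous; it does nothing for the death listing. The third is true, but case reporting is not an output of the study analysis.

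A reader might infer more than the documents support, in three ways.

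- **That these events reach no planned output at all.** This is too strong, given the wording of SAP 10.1 and 10.1.2 and the possible disposition count.
- **That most follow-up time goes unreported.** Treating the 15% dropout as never dosed gives 0.15 x 120 = 18 subjects and 18 x 336 = 6,048 subject-days, which looks large beside the few days between dosing and the final visit. The comparison fails. The documents do not say that dropouts are undosed subjects. Subjects who withdraw need not stay the full 336 days. On the same upper-bound basis the other 120 - 18 = 102 subjects contribute up to 102 x 336 = 34,272 pre-dose days, and their pre-treatment AEs are listed. SAP 12 also says that randomisation fell well short of plan.
- **That all procedure-related AEs could be listed from existing data.** Protocol 8.2.1.4 requires a link to procedures only for SAEs, and its causality categories concern study drug. Protocol 8.3.2 sends non-serious AEs to the AE eCRF only after the randomisation phase, while Protocol 6.1.2 lists the demonstration-patch practice before randomisation. Such a listing might need data that the plan does not secure.

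**Conclusion.** The point holds for deaths by the plain words of SAP 10.1.3: a death in a randomised subject who never doses is collected and then left out of the death listing. For SAEs, the general rules on their natural reading exclude the same subjects, but SAP 10.1 and 10.1.2 leave it open. What is established there is that the plan does not tell the programmer whom to include.

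The size is one listing for certain and a second possibly. No efficacy result, by-arm safety summary or treatment comparison changes. The documents give neither the number of never-dosed subjects nor an event rate, so no expected number of omitted events can be stated, and the report is incomplete only if such an event occurs. The conclusion rests on the text and on the possibility that at least one randomised subject does not dose. It does not depend on the dropout assumption.

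**What to change.** - **Protocol 7.1 and SAP 10:** keep treatment-emergent AE tables and by-arm safety summaries on the Safety population, as treated. State that the death and SAE listings are exceptions.
- **SAP 10.1.2 and 10.1.3:** have both listings cover every enrolled subject from consent, including SAEs recorded as linked to study procedures under Protocol 8.2.1.4. Say that enrolled means having signed the consent form.
- **Flag each event** as not dosed, before patch or after patch. The CRF question on whether the AE preceded patch administration separates the last two, and Safety population membership identifies the first.

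No listing of non-serious procedure-related AEs is asked for.

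The cost is wording and a population filter in two listings. Deaths and SAEs are already required on the AE eCRF page, so no new data are needed.

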7.2 Estimate of Sample Size

It is anticipated that 20% of subjects receiving placebo and 55% of subjects receiving active treatment will achieve pain relief at 15 minutes and sustained pain relief from 15 minutes to 60 minutes post-dose. Based on a two-sided chi-square test with continuity correction and an alpha level of 0.05, 40 subjects/arm will provide approximately 80% power to detect this same difference between two treatment groups, assuming a 15% dropout rate.

7.3 Demographic and Baseline Characteristics

Demographic and baseline characteristics such as age, gender, race/ethnicity, height, and weight, will be summarized by treatment group using descriptive statistics. Medical History will be coded using MedDRA and summarized by SOC and Preferred Term using frequency counts. Baseline disease characteristics will also be summarized.

7.4 Efficacy Analysis

7.4.1 Primary Analysis

The co-primary efficacy endpoints are the proportion of subjects who achieve pain relief at 15 minutes and the proportion who achieve sustained pain relief from 15 minutes to 60 minutes post patch application. These two endpoints will be analyzed separately using a Cochran Mantel Haenszel test stratified by cluster headache subtype (episodic or chronic) and will utilize the mITT population. A significance test of the treatment difference comparing each C213 dose to

placebo will be tested at the two-sided 0.05 level, and odds ratios and their corresponding 95% confidence intervals will be calculated. Headache pain will be assessed using a 4-point scale (0 = none, 1 = mild, 2 = moderate, 3 = severe), with pain relief defined by a decrease in pain from severe to mild or none without the use of acute rescue medication. Sustained pain relief requires a pain rating of mild or none at each timepoint from 15 minutes to 60 minutes without the use of acute rescue medication. Handling of missing data as well as sensitivity analyses will be described in the SAP.

7.4.2 Secondary Analyses

Secondary endpoints will be analyzed using similar methods as the primary endpoints and will utilize the mITT population.

To adjust for multiplicity and to control for overall type I error, a fixed sequential testing procedure will be applied to the primary analyses for the two C213 arms and the secondary efficacy analyses. If the primary efficacy analyses for the 3.8 mg arm both produce a result that is statistically significant at the 0.05 level, a significance level of 0.05 will be used for the primary analyses of the 1.9 mg arm and for the secondary efficacy analyses in an ordered fashion. If any subsequent analysis does not produce a statistically significant result at the 0.05 level, then the remaining analyses will automatically be considered non-significant. The order of testing for each endpoint and each C213 dose group will be provided in the SAP.

7.5 Safety Analysis

Safety analyses will be performed using the Safety population. Safety will be assessed by:

- Incidence of adverse events
- Physical exam including height and weight
- Vital signs including blood pressure
- Clinical laboratory determinations including serum chemistries and hematological parameters
- Pregnancy testing for women of child-bearing potential
- 12-lead ECGs
- Assessment of concomitant medications
- Investigator visual skin assessments

Adverse events will be coded using the latest version of MedDRA and will be summarized overall and by preferred term and system organ class. Adverse events will also be summarized by severity and relationship to study drug. Serious AEs and AEs leading to discontinuation of study drug will also be summarized.

All safety data will be listed by subject and parameter, separate listings of all abnormal laboratory findings and ECG findings will be provided, and clinically significant abnormalities will be recorded as AEs. Additional safety analyses will be described in the SAP.

8 ADVERSE EVENTS

All systemic and skin AEs, regardless of treatment group or suspected causal relationship to the investigational products, will be reported as described in the following sections.

For all systemic and skin AEs, the investigator must obtain adequate information both to determine the outcome of the AE and to assess whether it meets the criteria for classification as a SAE (see Section 8.2.1.1) requiring immediate notification (within 24 hours) to the Medical Monitor (MM) and Pharmacovigilance Group (PV) by completing a SAE Report Form. Sufficient information should also be obtained by the investigator to determine the causality of the AE, since he/she is required to assess causality. For systemic and skin AEs with a causal relationship to the investigational product, including **all** application site reactions, investigator is required to follow-up until the event or its sequelae resolve or stabilize at a level acceptable to the investigator, and Zosano Pharma concurs with that assessment.

Pregnancy: In the event that a pregnancy occurs, it will not be considered an AE but requires notification within 24 hours of investigator awareness to the Medical Monitor and Pharmacovigilance Group by completing a Pregnancy Report Form. The investigator will follow the pregnancy through the time of birth and report the outcome. Information about the subject's newborn or subject's pregnant partner will be followed for up to 1 month after the birth.

